4.2 Managing Infusion Reactions

Although infusion reactions were not observed in the Phase 1 and Phase IIa clinical trials, there is a theoretical potential for CD24Fc to result in infusion reaction. CD24Fc, which includes a human portion IgG1 may induce Fc γ R cross-linking, which has been associated with infusion reactions for some therapeutics.

Supportive care and vitals monitoring (including but not limited to supplemental oxygen, diphenhydramine, acetaminophen, ibuprofen, steroids and fluids) in the event of infusion reaction will be allowed and be dictated per institutional standards and policies. Depending on the severity of the infusion reactions, patient might be resumed the study drug at the discrepancy of the treatment physician. Patient will be permanently discontinued from the study if infusion reactions recur despite of pre-medications.

4.3 Ventricular Tachycardia

In the phase 1 first in human clinical trial a SAE of ventricular tachycardia was observed in one healthy individual that received 60mg of CD24Fc. Though this was considered mild in severity by the investigator and did not result in discontinuation of the subject from study, patient undergoing CD24Fc will be closely monitored for cardiac SAE.

Vital signs will be checked at immediately before and after each infusion of CD24Fc. EKG will be done before and after receiving CD24Fc. If at any time an episode of arrhythmia develops during treatment, study drug should be held until resolution of SAE. If the reaction is considered severe (e.g. symptomatic, hypotension requiring urgent intervention) study drug should be discontinued.

5. SUBJECT SELECTION

Subjects with advanced/metastatic or recurrent solid tumors (stage IV) of any primary site, with emphasis on non-small cell lung cancer, melanoma, bladder, and breast cancer that is incurable with available therapies will be recruited from the UC Davis Comprehensive Cancer Center ([Appendix 5](#)).

5.0 Inclusion Criteria

Patients must meet all of the following criteria to be eligible for study entry.

- 1) Ability to understand and willingness to sign an informed consent form.
- 2) At least 18 years of age.
- 3) Histologically confirmed advanced solid tumors.

- 4) Patients must have grade 2 or 3 irAEs from at least one ICI-containing regimen. Both newly emerging and persistent irAEs are allowed. Systemic steroid therapy or any other form of immunosuppressive therapy for irAEs is allowed. The specific irAEs are:
 - a. Grade 2-3 Diarrhea/Colitis: Patients with ≥ 4 stools per day or moderate-severe increase in ostomy output compared to baseline but not life-threatening diarrhea;
 - b. Grade 2-3 Pneumonitis: Mild to moderate (grade 2) or severe (grade 3) symptoms (including hypoxia, shortness of breath, requiring oxygen) but not life-threatening respiratory compromise requiring urgent intervention (e.g., tracheostomy or intubation)
 - c. Grade 2-3 Renal irAE: Creatine increased between 1.6-6.0 x ULN or ≤ 3.0 x baseline if baseline was abnormal, eGFR or creatinine clearance ≥ 15 ml/min/1.73m² but not life-threatening consequences or requiring dialysis.
 - d. Grade 2-3 Hepatic irAE: AST/ALT/ALP levels 3-20 x ULN, and T bilirubin increased ≤ 5 x ULN
 - e. Grade 2-3 Skin Rash: moderate (10-30% body surface area, BSA) to severe ($>30\%$ BSA) but not life-threatening skin lesions or Stevens-Johnson syndrome.
- 5) ECOG performance status <2 . ([Appendix 1](#)).
- 6) Life expectancy of ≥ 3 months at the time of enrollment.
- 7) All patients must have a pretreatment absolute neutrophil count (ANC) $\geq 1,000$ / μ L, hemoglobin ≥ 8 gm/dL and a pretreatment platelet count of $\geq 75,000$ / μ L obtained within 14 days prior to 1st dose of treatment.
- 8) Female subjects who are of non-reproductive potential (i.e., post-menopausal by history – no menses for ≥ 1 year; OR history of hysterectomy; OR history of bilateral tubal ligation; OR history of bilateral oophorectomy). Or, female subjects of childbearing potential must have a negative serum or urine pregnancy test within 72 hours prior to the first study drug administration.
- 9) Male and female subjects who agree to use highly effective method of birth control (e.g., implants, injectables, birth control pills with two hormones, intrauterine devices [IUDs], complete abstinence or sterilized partner, and female sterilization) and a barrier method (e.g., condoms, vaginal ring, sponge, etc.) during the period of therapy and for 90 days after the last dose of study drug.

5.1 Exclusion Criteria

Patients who meet any of the following criteria will be excluded from study entry.

- 1) Prior CD24Fc Therapy.
- 2) Any known active hepatitis B (HBV), hepatitis C (HCV), or human immunodeficiency virus (HIV) or acquired immunodeficiency syndrome (AIDS)-related illness, including patients who have an active infection requiring systemic therapy. History of COVID-19 or known asymptomatic carrier of SARS-CoV-2 virus is allowed.
- 3) Pregnant or lactating women.
- 4) Any medical condition including additional laboratory abnormalities, or psychiatric illness that would, in the opinion of the investigator, prevent the subject from participating and adhering to study related procedures.
- 5) Any known severe bacterial, fungal, or viral infection that in the opinion of the investigator would interfere with patient safety or compliance on trial within 2 weeks prior to enrollment.

- 6) Patients with concomitant proarrhythmic medications. (Appendix 6).
- 7) Patients with heart failure in NY Heart Association class IV.
- 8) Any grade 4 irAE symptoms and CTCAE v5.0 grade 4 toxicity. ([Appendix 4](#))
- 9) Renal, liver and cardiac toxicities as defined below:

Hepatic	AST, ALT, GGT, or ALP	>20.0 x ULN regardless of baseline
	Blood Bilirubin	>5.0 x ULN regardless of baseline
Renal	Creatinine	> 6.0 x ULN or creatinine clearance <15 ml/min/1.73m ²
	Urine: Anuria	<140 ml in 24 hours
Electrolytes	Hyponatremia, sodium	<120 mmol/L
	Hypokalemia, potassium	<2.5 mmol/L
Cardiac	CPK	>10.0 ULN
	ECG	Prolonged QT interval \geq 480mS, corrected by Fridericia's formula. Torsade de pointes; polymorphic ventricular tachycardia; signs/symptoms of serious arrhythmia.

6. STUDY DESIGN AND RULES FOR INFUSION SERIES CONTINUATION

This is a study at the University of California, Davis Comprehensive Cancer Center (UCDCCC). Registration and assignment to the repeated infusions will be done centrally at UCD. ([Appendix 2](#) and [Appendix 3](#)).

Rules for dosage/infusion continuation and termination are given below.

6.0 Screening Phase

All patients being considered for this trial will be pre-screened prior to protocol therapy for the following:

Patients who meet the above criteria (in addition to those outlined in section 3.0) will be deemed eligible for protocol therapy.

6.1 Treatment Phase

This is a phase I/II study to determine the safety, tolerability, and efficacy of CD24Fc in patients who needed treatment interruption from irAE with ICI. This study will be divided into two studies. Phase I study is to evaluate safety and tolerability of CD24Fc for treatment of irAE. Phase II consists of a randomized control study evaluating efficacy of CD24Fc in reducing duration of irAE and rate of recovery from irAE.

6.1.0 Phase I Safety Study

In the Phase I study, patients with unresectable or metastatic solid tumors who developed grade 2-3 irAEs and treatment interruption to immunotherapy will be selected for treatment. Once enrolled, CD24Fc will be administered every 2 weeks along with standard of care (i.e., steroids per treating physician and best supportive care) for 3 treatments. All 6 patients shall complete 3 treatments. For treatment dosing and schedule see [Table 1](#) and [Figure 1](#). Patients may receive steroids at the discretion of the treating physician prior to and during treatment with CD24Fc. Two weeks after completing dose 3 of CD24Fc (Day 42) patients will be re-evaluated for resolution of irAE. At the discretion of the treating physician patient can be evaluated for retreatment with ICI at this time. Patient will undergo end of study evaluation on day 60. Post study irAE and survival follow up will consists of chart check every 3 months for up to 1 year.

6.1.1 Phase II Randomized Double Blind Placebo Controlled Study

Phase II study will consist of a randomized double blind placebo controlled study involving patients who have treatment interruption due to grade 2 or 3 irAEs. Patients may receive steroids at the discretion of the treating physician prior to and during treatment with CD24Fc. As the steroids is the most commonly used SOC therapy for irAEs and it affects the severity and duration of irAE, we will separate the subjects into two groups based on the status of steroids use at registration. Each group of patients will be randomized (1:1) to receive CD24Fc vs placebo in addition to SOC treatment for irAE. Patients who are randomized to treatment with CD24Fc will receive treatment every 2 weeks for total of three treatments. Placebo group will receive 100 mL of normal saline every 2 weeks for total of three treatments. Refer to [Table 2](#) and [Figure 2](#) for treatment schedule. All patients shall complete 3 treatments.

Two weeks after completing the third treatment dose, patients will be re-evaluated for retreatment with ICI at the discretion of the treating physician and post treatment re-evaluation. Thereafter, patients will continue to end of treatment safety follow up on day 60. After the end of treatment, we will follow patients with irAE and survival by chart check every 3 months for up to 1 year.

6.2 Serum Sample Collection

During active treatment with CD24Fc CBC and CMP will be collected based on schedule see [Tables 1](#) and [2](#).

6.3 Drug Administration and Monitoring

CD24Fc or placebo will be administrated by intravenous infusion over 60 minutes.

Vital sign monitoring before the dosing, during and 1-hour post infusion by registered nurse per institutional standard.

If the patient misses a dose, an infusion would be rescheduled within 3 days. Otherwise, the dose will be omitted.

6.4 Dose modification based on laboratory values

6.4.0 Renal Function

If estimated GFR is less than 15 mL/min on the scheduled day of dosing, then the dose be held. If GFR recovers to greater than 15 mL/min within the protocol defined treatment period window (up to day +3), then CD24Fc may be resumed.

6.4.1 Hepatic Function

CD24Fc will be administered on the scheduled day if AST or ALT is ≤ 20 x ULN and total bilirubin is ≤ 5 x ULN.

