6. The PK/PD, ADA, correlative blood sample collection: 2x 10ml EDTA samples at each time point. The samples should be collected pre-dosing and 30±10 min after each IV infusion. Sample collection must be from the opposite arm to that used for study drug infusion.
7. Women of childbearing age only

[figure not shown]
Figure 2: Phase II Randomized, Placebo Controlled Study Schema

Table 2. Flow Chart for Phase II Study (CD24Fc Group vs Placebo Group)

CD24Fc 480 mg on day 1, 240 mg on day 14, and 240 mg on day 28 i.v. (a total course=28 days)							
Trial Period	Screening	Treatments			Post-Treatment	End of Study	Post-Study
Dose/Treatment Number		1	2	3	2-week Evaluation	Safety Follow Up	Survival Follow Up
Day	-14 to -1	1	14 ± 3	28 ± 3	42 ± 3	60 ± 3	Every 3 months to 1 year ¹
Drug Dispensation							
CD24Fc		X	X	X			
Placebo		X	X	X			
Administrative Procedures							
Eligibility evaluation, informed consent, medical history	X						
Medication review	X	X	X	X	X	X	X
Post-study status, survival status							X
Clinical Procedures							
Full physical exam	X				X	X	
Directed physical exam		X	X	X			
ECOG PS, vital signs, EKG ² , acute AE monitoring ³	X	X	X	X	X	X	
Evaluation for ICI retreatment					X		
Toxicity assessment (NCI CTCAE V5.0)	X	X	X	X	X	X	X ⁴
Laboratory Procedure/Assessment							
CBC with differential, CMP	X	X ⁵	X ⁵	X ⁵	X	X	
Correlative blood and plasma sample collection, PK/ADA samples ⁶		X ⁶	X ⁶	X ⁶	X	X	
Pregnancy test (urine or serum b-HCG) ⁷	X						

1. Frequency of follow-up office visits at the discretion of treating physician. Chart check every 3 months for post treatment and survival status. To continue until death or up to 1 year after completion of the study.
2. On days of CD24Fc administration, vitals and EKG will be obtained prior to and post infusion of study drug.
3. All patients will be monitored for 1-hour post infusion with a registered nurse or nurse practitioner within immediate proximity.
4. If irAE has not resolved to ≤grade 1 at day 60, check on primary oncologist's document for the grade of AE at every visit until resolution.
5. CBC and CMP blood draw should be within 3 days prior to CD24Fc administration
6. The PK/PD, ADA, correlative blood sample collection: 2x 8 ml EDTA samples at each time point. For all infusions, the samples should be collected pre-dosing and 30±10 min after IV infusion and the end of study visit. Sample collection must be from the opposite arm to that used for study drug infusion.

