4.1 Phase I Dose Limiting Toxicities

- 1) Grade 4 non-hematologic toxicity (not laboratory).
- 2) Grade 4 hematologic toxicity including Grade 4 neutrophil count decrease, Grade 4 platelet count decrease or Grade 4 anemia regardless of duration.
- 3) Grade 3 Neutrophil count decrease lasting > 1 week, or febrile neutropenia.
- 4) Grade 3 Platelet count decrease lasting > 1 week, or Grade 3+ thrombocytopenia with bleeding.
- 5) Grade 3 non-hematologic toxicity (not laboratory) will be considered a DLT with the following exceptions: grade 3 fatigue, Grade 3 nausea, vomiting, or diarrhea lasting < 72 hours, (Grade 3 nausea, vomiting, or diarrhea lasting >72 hours despite optimal supportive care is a DLT).
- 6) Any Grade 3 non-hematologic laboratory value if:
 - Associated with clinical symptoms or signs, or
 - Medical intervention is required to treat the patient, or
 - The abnormality leads to hospitalization, or
 - The abnormality persists for >1 week.
- 7) AST and/or ALT elevation >20 x ULN with concurrent total bilirubin elevation to >5 x ULN

without initial evidence of cholestasis.

8) Grade 5 toxicity (i.e., death).

The treatment related toxicities should be evaluated as CD24Fc treatment emergent AE that is not associated to irAEs defined in enrollment. The DLT monitoring period is the 14 days after the first dose of CD24Fc at 480 mg. If DLT occurred in 2 patients during the first dose of CD24Fc dosing in the 14-day period, CD24Fc will be reduced to 240 mg as first dose, or 120 mg until no more than 1/6 patients developed DLT. The study will be terminated if >2 patients have DLT at this reduced dosing. In Phase I, patients will be dosed at least two hours apart and no more than two patients will be enrolled in the same day.

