6.4.2 Hematologic laboratory values

CD24Fc will be administered on the scheduled day if absolute neutrophil count (ANC) $\geq 1,000$ / μ L, hemoglobin ≥ 8 gm/dL and a pretreatment platelet count of $\geq 75,000$ / μ L.

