6.7 Criteria for Removal from Protocol Treatment

- Unacceptable toxicity (as determined by the treating physician and/or the patient), or toxicity requiring discontinuation of treatment (See sections 4.0 and 4.1).
- Elevation in AST or ALT $>20x$ ULN on bloodwork prior to CD24Fc treatment.
- Elevation of total bilirubin $>5x$ ULN on bloodwork prior to CD24Fc treatment.
- If the recovery of any $\geq G3$ hematologic or non-hematological toxicity due to CD24Fc to grade 1 or less requires > 2 weeks.
- Patients may choose to withdraw from the study at any time for any reason.
- Patients may be withdrawn from the protocol at the investigator's discretion if the investigator feels that continuation is not in the patient's best medical interest or if the patient is non-compliant with treatment.
- Completion of treatment CD24Fc.
- All reasons for discontinuation of treatment must be documented in the case report forms.
- Therapy after Protocol Treatment is stopped: If patients fail to respond to the protocol treatment and/or are removed from the therapy because of toxic effects or "disease progression", further treatment, if any, is at the discretion of the investigator.

Follow-up off Protocol Treatment: After removal from protocol treatment, all patients will be followed for late toxicities. Patients will be seen 4 weeks, 4 months and 7 months after coming off therapy. If ongoing toxicities have not resolved to \leq grade 1 within the first 4 weeks, patients are to be seen every month until toxicity resolves to \leq grade 1. No new toxicities after the 4-week follow-up will be re-reported unless considered related to protocol treatment by the investigator.

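### Section 6.4.1, read literally, clears dosing when only one of AST and ALT is within 20 x ULN; Section 6.7 removes the same patient

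*Combined protocol and SAP*

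**What the plan says.** Four places in the protocol use 20 x ULN for transaminases as a cut-off for dosing, removal, exclusion or dose-limiting toxicity (DLT).

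- **Section 6.4.1 (dosing):** "CD24Fc will be administered on the scheduled day if AST or ALT is" at or below 20 x ULN and total bilirubin is at or below 5 x ULN.
- **Section 6.7 (removal from protocol treatment):** "Elevation in AST or ALT" above 20 x ULN on bloodwork before treatment. A separate bullet, "Elevation of total bilirubin", applies above 5 x ULN.
- **Section 5.1, exclusion 9:** the hepatic row lists "AST, ALT, GGT, or ALP" above 20 x ULN, so any one enzyme disqualifies. Bilirubin above 5 x ULN also excludes.
- **Section 4.1, DLT item 7:** "AST and/or ALT elevation" above 20 x ULN, but only with concurrent bilirubin above 5 x ULN and no initial evidence of cholestasis.

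Footnote 5 to Tables 1 and 2 fixes the timing of the laboratory draw: "CBC and CMP blood draw should be within 3 days prior to CD24Fc administration". Section 4.0 sends the reader to Section 6.4 for dose modification on hepatic values. Section 6.4.1 does not refer to 6.7, and no sentence says which of the two prevails.

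**The concern.** In a rule that stops treatment, *or* is the right connective: one enzyme over the limit is enough to stop. The matching rule that permits treatment needs *and*: every enzyme must be within the limit. Section 6.4.1 turns the inequality round but keeps *or*, so one acceptable transaminase offsets an unacceptable one.

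What is at stake is the consistency of a patient-safety rule. For one pattern of results, two subsections of Section 6 give opposite instructions: infuse, or take the patient off protocol treatment. The rule is relevant to this population, because hepatic irAE with AST/ALT/ALP of 3 to 20 x ULN is a qualifying event under inclusion criterion 4d, so some patients may enter close to the limit.

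**Working it through.** This is a check of logic. The plan states no figure to reproduce.

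**Rules as written** (multiples of ULN)

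- 6.4.1, literal: dose if (AST ≤ 20 or ALT ≤ 20) and bilirubin ≤ 5.
- 6.7, hepatic criteria: remove if AST > 20 or ALT > 20 or bilirubin > 5.
- 6.4.1, corrected: dose if AST ≤ 20 and ALT ≤ 20 and bilirubin ≤ 5.

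**All eight combinations**

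| AST | ALT | Bilirubin | 6.4.1 literal | 6.7 | Conflict | 6.4.1 corrected |
|---|---|---|---|---|---|---|
| ≤ 20 | ≤ 20 | ≤ 5 | dose | stay | no | dose |
| ≤ 20 | ≤ 20 | > 5 | no dose | remove | no | no dose |
| ≤ 20 | > 20 | ≤ 5 | dose | remove | **yes** | no dose |
| ≤ 20 | > 20 | > 5 | no dose | remove | no | no dose |
| > 20 | ≤ 20 | ≤ 5 | dose | remove | **yes** | no dose |
| > 20 | ≤ 20 | > 5 | no dose | remove | no | no dose |
| > 20 | > 20 | ≤ 5 | no dose | remove | no | no dose |
| > 20 | > 20 | > 5 | no dose | remove | no | no dose |

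The literal rule conflicts with 6.7 in 2 of 8 combinations, both with exactly one transaminase over the limit and bilirubin within it. The corrected rule conflicts in 0 of 8. It also leaves 0 of 8 in which a patient is neither cleared nor removed, so it is the exact negation of the hepatic criteria in 6.7.

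**Example with assumed values:** AST 25, ALT 15, bilirubin 1.

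- 6.4.1, literal: 15 ≤ 20 and 1 ≤ 5, so dose.
- 6.7: 25 > 20, so remove.
- Exclusion 9 in 5.1: 25 > 20, so the patient would not have been admitted with this result.
- DLT item 7: its transaminase part is met (25 > 20), but bilirubin of 1 is not above 5, so the item does not catch this patient.
- 6.4.1, corrected: 25 > 20, so no dose.

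The eight rows count logical combinations, not patients, so 2 of 8 is not a frequency.

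**The case against.** The best defence is that 6.4.1 is one check among several and does not by itself order an infusion. Section 6.4.2 opens in the same form, "CD24Fc will be administered on the scheduled day if absolute neutrophil count (ANC", and nobody would take it to mean that adequate blood counts justify dosing whatever the liver values. The introduction to Section 6 puts these subsections in one rule set: "Rules for dosage/infusion continuation and termination are given below". On that view a patient who passes 6.4.1 and fails 6.7 is simply not dosed, and the stricter rule governs. In ordinary usage, *AST or ALT is within the limit* can also mean that each of them is.

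Much of this stands. It shows that the intent is clear and that a site applying both sections would act correctly, which is why the point is minor. It does not make the two sentences consistent. The other checks in 6.4 concern renal function and blood counts and cannot detect this hepatic pattern, so the protection comes from 6.7 alone. A dosing rule should not depend on a colloquial reading when Section 4.1 already words the same comparison more carefully.

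Two smaller points are fair. Section 6.4.1 names no blood draw, so it is an inference, from 6.7 and footnote 5, that both rules are read from the same result. And inclusion criterion 4d also uses the 20 x ULN limit, with slashes that do not say whether one or all enzymes must be in range, so the wording elsewhere is not perfectly uniform. Neither point affects the comparison of 6.4.1 with 6.7.

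**Conclusion.** The point holds at low severity. It is an internal inconsistency of wording; nothing suggests that anyone chose to let one enzyme offset the other. It is confined to patients with exactly one of AST and ALT above 20 x ULN and total bilirubin at or below 5 x ULN. It rests on a literal reading of *or* in 6.4.1 and on both rules being applied to the same pre-dose result. The documents give no information on how common the pattern is, so its frequency is unknown. Harm would require a site to follow 6.4.1 literally and overlook 6.7. Sample size, power, type I error and the planned analyses are untouched.

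**What to change.** Reword 6.4.1 so that the scheduled infusion is given only if both AST and ALT are ≤ 20 x ULN and total bilirubin is ≤ 5 x ULN. Sections 4.1, 5.1 and 6.7 need no change for this purpose. The cost is a few words in one sentence, with no effect on visits, sample size or analysis.

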6.4.2 Hematologic laboratory values

CD24Fc will be administered on the scheduled day if absolute neutrophil count (ANC) $\geq 1,000$ / μ L, hemoglobin ≥ 8 gm/dL and a pretreatment platelet count of $\geq 75,000$ / μ L.

6.4.3 Dose adjustment

There should be a one level dose reduction (i.e., CD24Fc 240 mg on day 1, 120 mg on day 14, and 120 mg on day 28 i.v.) if any \geq G3 hematologic due to CD24Fc that requires < 2 week to recover to grade 1 or less. There will be no dose reduction according to irAEs.

6.5 Concomitant Therapy

Concomitant ICI and chemotherapies are not allowed during the study period.

Patients may receive ongoing supportive and palliative care (e.g., nutritional support, pain control) as clinically indicated throughout the study. Bisphosphonate therapy is allowed as part of supportive care before or after the study. Steroids are permitted in the study as outline in section 6.2. Patients enrolled to the study will receive steroid treatment as well as other recommended treatment for a given irAE if recommended per the treating physician. Patients who develop urgent complications in previously documented sites of disease may receive palliative radiation therapy. Continuation on the protocol therapy will be determined by discussions with the sponsor and the investigator, if medically appropriate.

